8.2. Subject Enrollment

Up to 500 subjects will be enrolled in this registry from up to 15 sites in Singapore, Thailand and Vietnam.

Subjects may be enrolled in this registry from the point of arrival at the enrolling hospital for treatment of their index stroke with a Medtronic market-released neurothrombectomy device, up to the day of hospital discharge or ≤7 days post index procedure, whichever comes first. The day of discharge is considered to be the date the subject is initially discharged from the acute hospital to home, rehab (even within same facility), etc. A subject is considered enrolled when informed consent is obtained and the subject has satisfied all eligibility criteria.

PR-NV-13514

Version A (13-MAR-2017)

Page 19 of 42

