8.1. Study Population

The registry population consists of subjects that have suffered an AIS due to large intracranial vessel occlusion who are treated with a Medtronic market-released neurothrombectomy device within 8 hours of stroke symptom onset.

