8.3. Inclusion Criteria

- 1. Subject/subject's legally authorized representative has given Informed Consent according to country regulations, and/or EC requirements.
- 2. Subject has experienced an Acute Ischemic Stroke due to large intracranial vessel occlusion in at least one of the following intracranial vessels: internal carotid artery (ICA), M1 and M2 segments of the middle cerebral artery (MCA), basilar, and vertebral arteries.
- 3. Subject has been or will be treated with a Medtronic market-released neurothrombectomy device as the initial device used to remove the thrombus.
- 4. Subject is willing to participate in a 90-day follow-up.
- 5. Treatment within 8 hours of stroke symptom onset (defined as stroke onset to access puncture).

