9.2. Subject Screening

Given that the prospective study population consists of patients who have or will undergo treatment with the use of a Medtronic market-released neurothrombectomy device and that the screening assessments consist of standard patient diagnostics for this therapy, subjects are considered enrolled in the study once the subject has signed and dated the informed consent. If the subject signs the Informed Consent form and is identified later as failing to meet all eligibility criteria, the subject will be classified as a screen failure. Upon determination that the subject does not qualify for enrollment, the reason for the subject's screen failure status will be documented on a Screening and Enrollment Log, in order to minimize bias. No eCRFs in the Electronic Data Capture (EDC) system are required to be completed for screen failure subjects.

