9.4. Subject Consent

The Principal Investigator or his/her authorized designee will conduct the informed consent process and ensure the nature and objective of this registry is thoroughly explained to the subject and/or subject's legally authorized representative (LAR) in the language understood by the subject/subject's LAR. The subject must have ample time and opportunity to read and understand the ICF, to inquire about details of the study, and to decide whether or not to participate in the clinical study. All questions about the study should be answered to the satisfaction of the subject. Language used should be non-technical and should not waive or appear to waive the subject's legal rights. The consent process can occur at any point during the enrollment period (from the point of arrival at the enrolling hospital where treatment for their index stroke with a Medtronic market-released neurothrombectomy device has occurred, up to the day of hospital discharge or ≤ 7 days post index stroke procedure, whichever comes first). The consent process will be done according to country regulations and/or IEC.

The Principal Investigator is responsible for ensuring informed consent form (ICF) is obtained from each subject and/or subject's LAR prior to subject enrollment and entering of any subject data into the registry database. Informed consent must be documented prior to any procedure specific to the clinical study is applied to the subject.

The ICF is required and must be obtained in a format approved by the IEC. The form should contain standard language consistent with local policies for ensuring privacy of confidential information. The ICF must be reviewed and approved by the Sponsor prior to submission to the appropriate IEC for approval.

PR-NV-13514

Version A (13-MAR-2017)

Page 22 of 42

The Investigator is responsible for ensuring any new information related to the registry will be provided to the subject and/or subject's LAR, if applicable. Subject may need to be re-consented to continue participation in the registry, as required by country regulations and/or IEC.

After all persons have signed and dated the informed consent form, the investigator must provide the subject with a copy of the signed and dated informed consent form.

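### Treated patients who die before consent may be missing from the cohort and need not be counted; this alone lowers reported 90-day mortality, but the net direction and size are unknown

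*Combined protocol and SAP*

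**What the plan says.** **Population.** Section 8.1 defines it by treatment: "The registry population consists of subjects that have suffered an AIS due to large intracranial vessel occlusion who are treated with a Medtronic" device within 8 hours of onset.

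**Entry.** Section 8.2 ties entry to consent: "A subject is considered enrolled when informed consent is obtained and the subject has satisfied all eligibility criteria". The window opens at hospital arrival and runs "up to the day of hospital discharge or ≤7 days post index procedure, whichever comes first"; section 9.4 repeats it. Criterion 3 in 8.3 covers both orders of events: "Subject has been or will be treated with a Medtronic market-released neurothrombectomy device as the initial device". Criterion 4 reads "Subject is willing to participate in a 90-day follow-up". A legally authorized representative may consent (8.3, 9.4). Section 9.4 requires consent "prior to subject enrollment and entering of any subject data into the registry database".

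**Outcomes.** All-cause mortality is counted from the procedure to 90 days (5.1.2.1). The primary endpoint is the mRS at 90 days (5.1.1.1), and deaths during follow-up are scored 6 (13.6).

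**Analysis set.** Sections 13.1 and 13.2 take enrolled subjects treated with a Medtronic device.

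**Accounting for those left out.** Section 9.2 describes one case: "If the subject signs the Informed Consent form and is identified later as failing to meet all eligibility criteria", the person is a screen failure, and "the reason for the subject's screen failure status will be documented on a Screening and Enrollment Log, in order to minimize bias". The disposition examples in 13.3 (completed, lost to follow-up) all arise after enrolment.

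**The concern.** The outcome clock starts at the procedure, but entry to the cohort can come up to seven days later. Someone enrolled after the procedure would ordinarily have had to survive until consent. Deaths in the gap may drop out of both numerator and denominator, and no required record would show that they existed.

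The registry is descriptive, and its sample size of 500 rests on no hypothesis test (13.5). Its product is a set of percentages, so the reader needs to know whom they describe. A larger sample does not shrink this kind of error. Section 13.4 also allows comparison or pooling with similar sponsor studies, where a difference in consent timing could pass for a difference in outcome. If sites never log these patients, the count may be hard to rebuild later.

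**Working it through.** There is no plan figure to reproduce: the documents give no mortality rate, no early-death rate and no distribution of consent times. Only two inputs come from them: n = 500 (13.5) and, as an example, 46% with mRS 0-2 (6.2, pooled trials). mRS 0-2 is not a named endpoint here. All other inputs are assumptions.

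**1. Direction of this mechanism alone.** Let M be true 90-day mortality among eligible treated patients and f the share who die before consent and are not enrolled.

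- Reported mortality = (M - f)/(1 - f), which is too low by f(1 - M)/(1 - f). This is positive for any f > 0 with M < 1.
- The share in any group of grades below mRS 6, true value G, reads G/(1 - f), which is too high.

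**2. Model for f.** f = (1 - p) x e x K, where

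- p = share consenting before the procedure;
- e = risk of death in days 0-7;
- K = mean chance that an early death precedes consent.

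Assumed pairs (M, e): 15% and 4 points; 16% and 6; 20% and 8.

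- Base case: deaths even over days 0-7, post-procedure consents even over days 0.5-7 (late, since enrolment closes at discharge if that is earlier). K = 3.75/7 = 0.536.
- Consents even over days 0.5-3: K = 1.75/7 = 0.250.
- Front-loaded deaths (rate 0.5 per day, within day 7), consents as in the base case: mean of exp(-0.5c) over consent day c = (exp(-0.25) - exp(-3.5))/(0.5 x 6.5) = 0.230; K = (1 - 0.230)/(1 - exp(-3.5)) = 0.794.

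The model treats every death before consent as lost; it has no term for representative consent after death.

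**3. Results.** Middle case with p = 0.5: f = 0.5 x 0.06 x 0.536 = 0.0161. Reported mortality = (0.16 - 0.0161)/(1 - 0.0161) = 14.6%, so 1.4 points low. Over the three pairs, points by which mortality reads low:

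| Consent before procedure | Base case | Consents by day 3 | Front-loaded deaths |
|---|---|---|---|
| 90% | 0.2-0.3 | 0.1-0.2 | 0.3-0.5 |
| 50% | 0.9-1.8 | 0.4-0.8 | 1.4-2.6 |
| None | 1.9-3.6 | 0.9-1.6 | 2.8-5.4 |

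Base case, 46% with mRS 0-2 would read 46.1-46.2% (90%), 46.5-47.0% (50%) or 47.0-48.1% (none).

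For scale, the 95% half-width at n = 500 is 1.96 x sqrt(0.1408 x 0.8592/500) = 3.0 points at 14.1% mortality and 1.96 x sqrt(0.1825 x 0.8175/500) = 3.4 points at 18.2%.

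**4. The opposite loss.** Suppose a share g of treated patients leave alive before consent and all survive to day 90.

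- Mortality shift cancels when (M - f)/(1 - f - g) = M, so g = f(1 - M)/M. Base case, p = 0.5: f = 1.07/1.61/2.14%, g = 6.1/8.4/8.6%.
- If 80% of them had mRS 0-2 (assumed), that shift cancels when 0.34g = 0.46f: g = 1.4/2.2/2.9%.

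**5. What a count would show.** Middle case, p = 0.5, 500 enrolled: 500/(1 - 0.0161) = 508 treated, 8 lost.

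- Enrolled only: 73/500 = 14.6% deaths; 234/500 = 46.8% with mRS 0-2.
- With the 8 deaths restored: 81/508 = 15.9%; 234/508 = 46.1%.
- With 20 further patients discharged before consent, outcome unknown: mortality 81/528 to 101/528 = 15.3-19.1%; mRS 0-2 234/528 to 254/528 = 44.3-48.1%.

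**The case against.** The plan has partial safeguards. A representative may consent, and section 9.1 has family or a representative supply the 90-day information when the subject is unavailable for any reason. So criterion 4 need not shut out a patient who has died, and the documents neither allow nor bar consent after death. This stands: the loss could be small or nil at some sites, and the figures above are upper values on that input.

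The log may already be wider than it looks. Section 9.2 requires entries for signed screen failures but does not confine the log to them, the 13.3 list is open-ended, and the log template and eCRFs are not in the documents. This stands too, so the point is that nothing requires the count, not that sites will fail to keep one.

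The size is assumed throughout, and at 50-90% consent before the procedure the base-case shift lies inside sampling error. That limits the weight of the point. It does not remove it, because without the count nobody can show whether the loss is zero or material.

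A reader might infer that the registry's results must look too good. The documents do not support that: enrolment also closes at discharge, and on the example scale losing 1.4-2.9% of treated patients as early-discharged survivors would cancel the mRS 0-2 shift.

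**Conclusion.** The gap is real on the text: treatment can precede consent, outcomes run from treatment, only enrolled subjects are analysed, and no passage requires a count of eligible treated patients who die or leave before consent. Certain by algebra, given any such loss, is that deaths missed in this way, taken alone, lower reported mortality and under-count mRS 6. The net direction and the size are not established. The range of 0.2-1.8 points (50-90% consenting before the procedure) to 1.9-3.6 points (none) rests on assumed mortality, assumed even timing and no consent after death; front-loaded deaths extend it to 5.4.

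Two further inferences should not be drawn. No direction follows for sICH. Nor do 9.4 (no data entry before consent), 11.2 (SAEs collected from groin puncture, reported within 24 hours of awareness) and 9.7 (late reports are deviations) clearly conflict: 11.2 speaks of subjects, so the duty can be read as starting at enrolment. A clarifying sentence there is optional.

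This is worth fixing because it costs little and may be hard to repair afterwards, not because a material bias has been shown.

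**What to change.** Leave the enrolment window and the primary analysis unchanged.

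1. In 9.2, where ethics rules allow, extend the Screening and Enrollment Log to anonymous counts of patients who met criteria 2, 3 and 5 and no exclusion but were not enrolled. Record the reason: death before consent, discharge before consent, refusal, site cap or other. Criteria 1 and 4 are left out of this definition because they depend on consent or willingness. Restricting it to otherwise eligible patients keeps out, for example, those in whom another device was used first.
2. In 13.3, report these counts beside the number enrolled.
3. In 13.4 and 13.6, add a sensitivity bound limited to two groups: deaths before consent, counted as deaths and mRS 6, and discharges before consent, with unknown outcomes set in turn to best and worst. Refusals and patients beyond the site cap are counted but stay out of the bound.

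The cost is slight site logging and a few lines of text. The bound widens with the number of unknown outcomes: 20/528 = 3.8 points for 20 per 500 enrolled in the middle case, and 50/558 = 9.0 points for an assumed 50. Its scope should therefore stay narrow.

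Reporting outcomes by consent timing is optional. It would be imprecise, and timing may itself depend on prognosis.

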8.3. Inclusion Criteria

- 1. Subject/subject's legally authorized representative has given Informed Consent according to country regulations, and/or EC requirements.
- 2. Subject has experienced an Acute Ischemic Stroke due to large intracranial vessel occlusion in at least one of the following intracranial vessels: internal carotid artery (ICA), M1 and M2 segments of the middle cerebral artery (MCA), basilar, and vertebral arteries.
- 3. Subject has been or will be treated with a Medtronic market-released neurothrombectomy device as the initial device used to remove the thrombus.
- 4. Subject is willing to participate in a 90-day follow-up.
- 5. Treatment within 8 hours of stroke symptom onset (defined as stroke onset to access puncture).

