5.1.2.2. Additional Evaluations

The following additional assessments for evaluation will be completed:

- Revascularization at the end of the procedure using mTICI score (0, 1, 2a, 2b, 3)
- Workflow metrics (e.g., time from onset to door, time from door to imaging, time from imaging to puncture, time from door to revascularization, etc.)
- Post-acute discharge disposition: discharge to home or any other type of facility (e.g. rehabilitation services, nursing facilities, hospice, etc.)
- National Institutes of Health Stroke Scale (NIHSS) score at hospital discharge or ≤ 7 days post index stroke procedure, whichever comes first.
- Subject disposition at study exit

6. Study Design

This is a prospective, multi-center, non-randomized, observational registry of AIS patients that have or will undergo treatment with the use of a Medtronic market-released neurothrombectomy device (as the initial device used to remove the thrombus) within 8 hours of stroke symptom onset. This registry aims to collect real world data on patients in whom the decision of device use has been made prior to data collection. This registry does not aim to affect patient care, but rather only to document outcomes observed during standard of care stroke management practice at investigation sites.

Methods incorporate to minimize bias were considered and up to 500 subjects will be enrolled at up to 15 sites in Singapore, Thailand and Vietnam. Each site is expected to enroll a minimum of 10 subjects, not to exceed a maximum of 75 subjects per site to ensure wide spread distribution of data. Sponsor approval must be obtained prior enrolling additional subjects.

All study clinicians and Medtronic/study personnel will be trained on the corresponding aspects of the study using standardized training materials and required to follow the CIP. Subjects may be enrolled in this registry from the point of arrival at the enrolling hospital where treatment with a Medtronic market-released neurothrombectomy device is to occur, up to the day of hospital discharge, or \leq 7 days after index stroke procedure, whichever comes first. The baseline through discharge visits will take place

PR-NV-13514 Version A (13-MAR-2017)

Page 16 of 42

Medtronic

at the treating hospital. Subject's participation in this prospective data collection registry will conclude at the completion of the 90-day follow-up.

An overview of the registry flow is depicted in Figure 1.

[figure not shown]

Figure 1. Registry Flowchart

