9.1. Schedule of Events

Assessments and procedures for stroke management will be performed in this registry as per standard of care. Subjects enrolled into the registry will follow the schedule of assessments to be performed at each study visit as listed in the **Table 2**.

PR-NV-13514

Version A (13-MAR-2017)

Page 20 of 42

Table 2. Visit and Assessment Schedule

	Enrollment				Follow-up
Visit	Baseline	Procedure	24 hrs Post Procedure	≤ 7 days or Discharge	90-Day
Range			± 8 hrs		± 15 days
Day	0	0	1	7-10	90
Method	Clinic Visit	Clinic Visit	Clinic Visit	Clinic Visit	Clinic Visit or Phone
Demographics and Medical History	*				
mRS Assessment	•¹			•	•
NIHSS Assessment	♦ ²		♦ 4	•	♦ 6
ASPECTS	♦ ³				
Mechanical Thrombectomy		♦ 5			
Adverse Events		•	•	•	•
Discharge Disposition				•	

- 1. Pre-stroke mRS is completed at baseline by obtaining verification from an individual aware of the subject's functional status prior to stroke (e.g., family member, friend, etc.), as per standard of care. Pre-stroke mRS should reflect the subject's condition just prior to stroke onset. For example, if the subject was hospitalized during stroke onset, the subject's reason for hospitalization should be taken into account when evaluating the subject's pre-stroke mRS.
- 2. Pre-treatment NIHSS closest to start of procedure, as per standard of care.
- 3. ASPECTS evaluated from baseline imaging at enrolling hospital, as per standard of care.
- 4. Post-procedure NIHSS should reflect the latest score within the 24 ± 8 hour post procedure window, as per standard of care.
- 5. Required for subject to be eligible for the study.
- 6. Assessment will not be performed if visit is completed via phone

90-day Follow-up

The 90-day follow-up will be conducted as an office visit or via phone by the Investigator or research staff to collect information related to the subject's mRS and overall clinical condition. If the subject is unavailable for any reason, the subject's family/relative or caregiver/ legally authorized representative will be requested to provide the applicable information. A subject's participation in this prospective data collection registry will conclude at the completion of the 90-day follow-up. A follow-up electronic case report form (eCRF) will be completed for every subject that is enrolled into this registry, including subjects who prematurely discontinue.

PR-NV-13514

Version A (13-MAR-2017)

Page 21 of 42

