9.5. Assessment of Safety

Assessment of safety shall be based on the following:

- Incidence of symptomatic Intracranial hemorrhage (sICH) at 24 hrs ± 8 hrs post procedure
 - o sICH: \geq 4 points worsening from baseline on the NIHSS scale associated with an image finding of intra-cranial hemorrhage (i.e. intracerebral or intraventricular) at 24 ± 8 hrs post procedure.
- All-cause mortality through 90 days post procedure
- Incidence of emboli in new territory (ENT) at 24 hrs ± 8 hrs post procedure
 - o ENT: Embolization territories outside of the target downstream territory

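### Enrolment may follow early outcomes: consent stays open to discharge or day 7, with no consecutive-approach rule and no count of treated patients

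*Combined protocol and SAP*

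**What the plan says.** Five parts of the combined protocol and SAP bear on this.

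- **Entry after treatment.** Inclusion criterion 3 in section 8.3 reads "Subject has been or will be treated with a Medtronic market-released neurothrombectomy device as the initial device used to remove the thrombus". On its own this is a device criterion. The timing comes from the next two places.
- **Enrolment window.** Section 8.2 opens enrolment at arrival and keeps it open "up to the day of hospital discharge or ≤7 days post index procedure, whichever comes first". The synopsis and section 6 give the same window.
- **Consent within the window.** Section 9.4 states: "The consent process can occur at any point during the enrollment period". The subject or a legally authorised representative may give it.
- **Bias control.** Section 6 says "Methods incorporate to minimize bias were considered and up to 500 subjects will be enrolled at up to 15 sites", followed by limits of 10 to 75 subjects per site and standardised training. Section 9.2 says "the reason for the subject's screen failure status will be documented on a Screening and Enrollment Log, in order to minimize bias". That entry is described for a person who signs consent and is later found ineligible.
- **Analysis set.** Sections 13.1 and 13.2 analyse enrolled subjects treated with the device. Section 13.4 adds that the data may be compared or pooled with similar sponsor investigations.

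**The concern.** A site can follow the enrolment rule to the letter and still decide whom to approach after seeing how the patient did. The early results are themselves reported by the registry (mTICI, sICH) or bear on the primary endpoint, 90-day mRS (NIHSS). If approach depends on them, the summaries describe the patients whom sites chose to enrol, not the patients treated. A larger sample does not reduce this error.

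A living patient who is never approached leaves no required trace, so no planned analysis could detect or correct the selection. Section 6.2 says this kind of evidence informs treatment decisions, coverage and guidelines, and pooling under section 13.4 would carry the selection into other analyses. Patients who die before consent raise a related but separate question, which is not counted here.

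**Working it through.** **Step 1. What is known before the window closes.**

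| Result | When known | Source |
|---|---|---|
| Final mTICI | End of procedure, day 0 | Section 5.1.2.2 |
| sICH | 24 ± 8 h, i.e. 16 to 32 h | Section 9.5: "Incidence of symptomatic Intracranial hemorrhage (sICH) at 24 hrs ± 8 hrs post procedure" |
| Post-procedure NIHSS | 16 to 32 h | Section 9.1, Table 2 note 4: "Post-procedure NIHSS should reflect the latest score within the 24 ± 8 hour post procedure window, as per standard of care" |
| Window closes | Discharge or day 7, whichever is first | Section 8.2 |

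Section 15.2 asks that the 24-hour NIHSS be routine at participating sites for all thrombectomy patients, so it is on the chart whether or not the patient is enrolled. All three results normally precede the close of the window. The exception is a patient discharged before the 24-hour results.

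**Step 2. Whether anything in the plan limits selection within a site.**

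- Sections 6, 8.2, 9.2 and 9.4: no rule to approach consecutive or all eligible treated patients.
- Section 9.2: the log entry applies after a signature, so it misses patients never approached and patients who declined.
- Section 9.7: reportable deviations concern consent, SAE reporting times and training, not selective enrolment.
- Section 6: site limits govern spread across sites, and training governs conduct. The statement that device use is decided before data collection protects treatment choice, not the choice of whom to enrol.
- Sections 13.1 to 13.6: no enrolled-to-treated ratio and no analysis by time of consent.

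**Step 3. The plan's own figures.** Section 13.5 gives 500 without power calculations, so there is no formula to reproduce. The one attached figure agrees: 75/500 = 0.15, the stated 15% site cap.

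**Step 4. Hypothetical size.** Inputs are p = 0.46 for mRS 0-2 at 90 days (section 6.2, from a pooled analysis of five randomised trials) and n = 500. The enrolment probabilities g (mRS 0-2) and b (mRS 3-6) are assumptions; the documents give none.

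Random half-width = 1.96 × √(0.46 × 0.54 / 500) = 0.0437, or 4.4 points.

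Observed proportion = 0.46g / (0.46g + 0.54b).

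| g | b | Calculation | Observed | Shift (points) |
|---|---|---|---|---|
| 0.70 | 0.60 | 0.322 / (0.322 + 0.324) | 49.8% | 3.8 |
| 0.70 | 0.50 | 0.322 / (0.322 + 0.270) | 54.4% | 8.4 |
| 0.80 | 0.50 | 0.368 / (0.368 + 0.270) | 57.7% | 11.7 |

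The mildest case lies inside the half-width. Setting the shift equal to the half-width gives g/b = (0.5037 × 0.54) / (0.46 × 0.4963) = 1.19.

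**Step 5. Why the real shift would be smaller for a given preference.** Nobody knows the 90-day mRS by day 7, so a site can select only on an early marker. Suppose patients with a good marker are enrolled with probability A and the others with probability B < A. Let shares s₁ of mRS 0-2 patients and s₀ of mRS 3-6 patients have a good marker. Then g = B + (A − B)s₁ and b = B + (A − B)s₀. The ratio g/b is below A/B unless the marker predicts perfectly (s₁ = 1, s₀ = 0). The figures in step 4 are therefore upper values for each pair of probabilities.

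**The case against.** The strongest reply is that entry after treatment is deliberate in an observational, descriptive registry, and that the text permits selection without showing that it occurs. Both points are right. They limit the claim to what could happen, but do not supply the missing rule or denominator.

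A reader might go further than the documents allow in four ways.

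- **That the bias must be favourable.** It is plausible, not certain. The window closes at discharge, which section 8.2 says includes a move to rehabilitation, so fast recoverers may leave before being approached while severely affected patients remain available. Representatives may consent, so incapacity does not bar entry. Enrolment from arrival, before any result, is also allowed.
- **That the screening log is the plan's only bias measure.** Section 6 sets site limits and training beside its bias statement. The log is the only control on individual selection.
- **That the 75-subject cap pushes busy sites to choose.** No site volumes are given. Over the 24-month enrolment period, 75 is about 3 a month (75/24 = 3.1). Section 6 can be read as allowing more with sponsor approval, and a capped site may simply stop sooner.
- **That nothing could be recovered later.** Consent forms are dated and the procedure is day 0, so consent timing by date can be found in source documents. The count of treated patients cannot be rebuilt from registry records.

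The magnitude also has limits. The 46% comes from trials that section 4.1 describes as anterior circulation stroke, while this registry also admits basilar and vertebral occlusions.

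**Conclusion.** The point holds as a gap in the design. The enrolment rule permits selection that depends on early outcomes, and the plan has neither a consecutive-approach requirement nor a treated-patient denominator to reveal it. The mRS, sICH and mTICI summaries could all be affected.

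The size is unknown. The shifts of 3.8 to 11.7 points rest on assumed enrolment probabilities tied to the 90-day outcome and on a 46% reference rate from a different population. They show only that moderate selection, with an enrolment ratio above about 1.19, could exceed the 4.4-point random error at n = 500. The documents do not support a statement that the registry is biased, or that the bias is favourable. The change should be made because the gap cannot be repaired once enrolment has passed without records of those not enrolled.

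**What to change.** - **Sections 6 and 8.2:** require each site to offer enrolment to every consecutive eligible patient treated with the device.
- **Section 9.2:** have each site keep a de-identified log with one line and a reason for each eligible treated patient not enrolled (for example not approached, declined, discharged first). Section 9.4 requires consent before any subject data enter the registry database, so the log must sit outside it and follow IEC and local rules.
- **eCRF:** record consent date and time relative to puncture.
- **Section 13.4:** report the enrolled-to-treated ratio by site. As a descriptive check only, tabulate mRS, mortality, sICH and mTICI by consent before or after the procedure. That comparison is confounded by severity and by whether a representative was available, so it cannot isolate selection.

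The cost is some protocol text, a log line per eligible treated patient not enrolled, a count of those treated, a consent-time field and the added tabulations. The downsides are a small site workload, possible IEC agreement for the log in three countries, and perhaps a small group consented before the procedure. Clinical care does not change.
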